#### **Inclusion Criteria:**

1. At least 50 years of age in Caucasians or 45 years of age in African-Americans.

2. Patients undergoing primary screening colonoscopy (either average risk or increased-risk) or surveillance colonoscopy after prior screening/surveillance colonoscopy.

3. Capable of understanding instructions, adhering to study schedules and requirements, and willing to provide informed consent.

#### **Exclusion Criteria:**

- 1. History of colectomy, partial or complete
- 2. Symptoms suggesting possible colorectal stenosis or cancer
- 3. Inflammatory bowel disease
- 4. Familial polyposis syndromes
- 5. History of, or current diagnosis of colorectal cancer
- 6. American Society of Anesthesia Physical Stats (ASA PS) score of IV or greater
- 7. Non-correctable coagulopathy
- 8. Currently receiving anti-thrombotic therapy, with an INR > 1.5
- 9. Poor prep, total BBPS score < 6, or any part of the colon < 2.
- 10. Patients with known allergy to peppermint oil or peppermint containing products.

11. Patients taking calcium channel blockers (Amlodipine, Nifedipine, Verapamil, Diltiazem, Dihydropyridine, Felodipine, etc).

**Product, Dose, Mode of Administration**: Peppermint oil solution will be prepared as described above in 20mL aliquots of 1.6% peppermint oil. A total of 4 separate 20mL aliquots will be provided in standard plastic syringes for patient who are randomized to the experimental arm of the trial. The placebo solution will be provided in the same fashion in 4 separate 20mL aliquots provided to those randomized to the placebo arm of the trial. The endoscopist will be required to inject the contents of the provided syringes through the endoscope at specific times during the procedure. The first dose will be delivered during the withdrawal portion of the exam in the cecum. After this the endoscopist should proceed with the exam as per standard procedure. A second dose will be delivered in proximal portion of the sigmoid colon. Up to two additional doses can be delivered at any time during the procedure as per the judgment of the endoscopist. Importantly, after injecting the 20mL of solution through the endoscope, the physician will also inject an additional 20mL air through the endoscope to ensure the complete dose was delivered. The endoscopists will note where all doses were delivered in the post procedure survey.

The dosing below and the protocol above has been approved by the FDA IND committee:

Each 20mL aliquot of experimental solution contains: 160mg L-Menthol (320mg Peppermint oil) The maximum delivered dose is 4 separate 20mL aliquots: 640mg L-menthol (1280mg peppermint oil).

The peppermint oil to be used in this study is produced by Now Foods® and purity data and manufacturing data has been provided to the FDA and this is part of the attached FDA IND application. As per the FDA IND committee recommendations, for the proposed trial, the pulegone (an agent shown to be hepatoxtic in animal studies) content of the clinical batch of peppermint oil to be used in the study must be known. As per the European recommendation for peppermint oil used in herbal medicine products, the batch must contain no more than 2.5% of pulegone. The official certificate of analysis showing the pulegone content for the batch of peppermint oil to be used during the study will be provided to the respective IRBs and the FDA, if needed.

**Additional Therapy, Dose, Mode of Administration:** ANY approved bowel prep, such as GoLYTELY® (Polyethylene glycol-3350 236 g, sodium sulfate 22.74 g, sodium bicarbonate 6.74 g, sodium chloride 5.86 g, and potassium chloride 2.97 g) 4 liters given orally the night before colonoscopy as bowel preparation or MoviPrep® (Polyethylene glycol-3350 100 g, sodium sulfate 7.5 g, sodium chloride 2.691 g, potassium chloride 1.015 g, sodium ascorbate 5.9 g, and ascorbic acid 4.7 g). Split-preps and extended-preps will be encouraged as per hospital protocol and clinical indication. Conscious sedation according to hospital protocol will be provided during colonoscopies as per standard practice.

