#### Methodology:

The institutional investigational pharmacy at each site will create and dispense a 1 liter solution containing 1.6% peppermint oil (solution A) or placebo (solution B). Once a patient consents for the procedure and is brought to the endoscopy room, research personel will selecte an opaque envelope that is serially numbered, labeled, and randomly assigned in a variable block fashion with a 1:1 ratio in blocks of 4 or 6 stratified by institution and indication for procedure (surveillance or screening). This contents of envelope will contain a paper assigning the patient to the either solution A or solution B. The research personal will draw up 20mL of this solution in each of 4 total plastic syringes. These syringes will be placed on the endoscopy cart to be used by the endoscopist during the procedure as described in the paragraphs below. Each site will also utilize an essential oil diffusing device in the endoscopy suite to mask any smells that could potentially confound blinding.

Solution A) Peppermint oil solution (1.6% peppermint oil, which is 0.8% L-menthol)

Ingredients:

- 1) 16mL of peppermint oil (provided by the NowFoods® company)
- 2) 0.4mL of Tween® 80 (i.e. Polysorbate 80) this is a commonly used food additive that acts as a surfactant to bring the peppermint oil into solution
- 3) 1L prepackage sterile water
- 4) 2.6mL of undyed simethicone

Instructions to prepare:

- 1) Add peppermint oil, tween, and simethicone to sterile water. Then, shake vigorously.
- Once solution has settled, and patient has been randomized, draw 20mL of solution into a plastic syringe
- 3) As a result, in our each syringe will contain **160mg of L-Menthol.**

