#### Solution B) Placebo solution

Ingredients:

- 1) 0.4mL of Tween® 80 (i.e. Polysorbate 80) this is a commonly used food additive that acts as a surfactant to bring the peppermint oil into solution
- 2) 1L prepackage sterile water
- 3) 2.6mL of undyed simethicone

Instructions to prepare:

- 4) Add tween and simethicone to sterile water. Then, shake vigorously.
- 5) Once solution has settled, and patient has been randomized, draw 20mL of solution into a plastic syringe

In the morning of the procedure, patients undergoing screening and surveillance colonoscopy will be pre-screened to evaluate if they meet inclusion criteria. Once patients are identified they will be approached by study personnel (consisting of PI, co-investigators, and additional staff supervised by the PI or co-investigators) to determine their willingness to participate in the study. If the subject is willing to participated, he or she will undergo written consent for participation in the study by research protocol personnel. Patients will be questioned regarding their allergy status specific to peppermint oil and this will be documented in the consent form and in the REDCap database.

Once the patient is willing to participate and inclusion/exclusion criteria are met based on prescreening in the EMR, which includes evaluation of prior baseline labs, designated research personnel (that will not be involved in the actual colonoscopy) will draw up 20mL of solution in each of 4 total plastic syringes. Placebo and experimental solutions will be similar in appearance. These syringes will be placed on the endoscopy cart to be used by the endoscopist during the procedure as described in the paragraphs below.

Endoscopy rooms being used for this study will use an essential oil diffuser to add olfactory blidning. As the experimental solution has a distinct odor of peppermint oil, the diffusing device will prevent olfactory detection by the endoscopist and staff.

Endoscopists and trainees working with supervising endoscopists will be provided with a total of four (4) 20mL prefilled syringes consisting of either solution A (1.6% peppermint oil, which is 0.8% L-menthol) or solution B (protocol). Both solutions are similar in appearance.

Endoscopists will be required to deliver 1 syringe at the cecum and 1 syringe in the sigmoid colon. Up to 2 additional doses can be delivered at the discretion of the endoscopist up to a maximum of 4 total doses (**max total dose = 640mg L-Menthol**).

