#### Risks and discomforts and how minimized:

1) Breech of privacy - The data, while securely stored, has a small risk to be breeched and is a risk to participating in this study.

2) There is a small risk of allergy to peppermint oil, and, if encountered, we will treat accordingly to standard care protocol.

The following steps will be taken to minimize these risks are:

1) Risks of confidentiality breech will be minimized using security features as previously defined including use of a secure, online database application (REDCap) and storage of hard-copy documents in a locked cabinet in the PI's locked office.

2) Risk of allergy to peppermint oil will be minimized by asking subjects prior to the procedure for known allergies to peppermint or its byproducts.

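### The allergy screen covers only peppermint, although both study solutions also contain polysorbate 80 and simethicone

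*Combined protocol and SAP*

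**What the plan says.** Three places in the combined protocol and SAP deal with allergy before dosing, and all three stop at peppermint:

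- Exclusion Criteria, item 10, excludes "Patients with known allergy to peppermint oil or peppermint containing products".
- The text on patient approach and consent, under the Solution B heading, states that "Patients will be questioned regarding their allergy status specific to peppermint oil", with the answer recorded in the consent form and in REDCap.
- The section on risks and discomforts names one allergy risk, "There is a small risk of allergy to peppermint oil", and reduces it by "asking subjects prior to the procedure for known allergies to peppermint or its byproducts".

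The preparation instructions describe more than peppermint. For solution A, under Methodology, they are "Add peppermint oil, tween, and simethicone to sterile water"; for solution B, "Add tween and simethicone to sterile water". The quantities of the two shared excipients are the same in both lists: "0.4mL of Tween® 80 (i.e. Polysorbate 80") and "2.6mL of undyed simethicone". Two 20 mL syringes are required for each patient and up to four are allowed.

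**The concern.** The protocol treats allergy to the study solution as a risk to be reduced by asking beforehand and excluding those who report it. It applies this to one of the three ingredients added to the water in solution A, and to neither of the two added in solution B. It gives no reason for leaving the others out.

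At stake is an avoidable exposure. Staff who follow the criteria exactly could enrol and dose a patient whose record shows an allergy to polysorbate 80 or simethicone, and no eligibility rule would have been broken.

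**Working it through.** This is a question of eligibility wording. No power or sample-size formula applies, and the plan gives no figure to reproduce. The check sets the ingredient lists against the criteria and then sizes the exposure.

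**Step 1: ingredients against the allergy screen**

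| Ingredient added to 1 L sterile water | Solution A | Solution B | Exclusion 10 | Allergy question | Risk section |
|---|---|---|---|---|---|
| Peppermint oil | 16 mL | none | covered | covered | covered |
| Polysorbate 80 | 0.4 mL | 0.4 mL | not covered | not covered | not covered |
| Simethicone | 2.6 mL | 2.6 mL | not covered | not covered | not covered |

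**Step 2: could another criterion close the gap?** None of the three inclusion criteria and none of the other ten exclusion criteria mentions allergy or hypersensitivity to polysorbate 80, simethicone or the study solution as a whole.

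**Step 3: could another procedure close it?** Patients are prescreened in the electronic record (Solution B section), have a standard history and physical examination (Criteria for Evaluation) and have their medical history reviewed by nursing staff (Plan for obtaining informed consent). Any of these could bring an allergy to light. None is linked to a rule that would exclude the patient.

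**Step 4: exposure per patient.** Assume that volumes add.

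- Batch volume, A: 1000 + 16 + 0.4 + 2.6 = 1019.0 mL
- Batch volume, B: 1000 + 0.4 + 2.6 = 1003.0 mL
- Excipient per 20 mL syringe = excipient volume × 20 / batch volume
- Polysorbate 80: A, 0.4 × 20 / 1019 = 0.0079 mL; B, 0.4 × 20 / 1003 = 0.0080 mL
- Simethicone: A, 2.6 × 20 / 1019 = 0.0510 mL; B, 2.6 × 20 / 1003 = 0.0518 mL

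| Syringes | Polysorbate 80, A / B (mL) | Simethicone, A / B (mL) |
|---|---|---|
| 2 (required) | 0.016 / 0.016 | 0.102 / 0.104 |
| 4 (maximum) | 0.031 / 0.032 | 0.204 / 0.207 |

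The amounts are small but not zero. The arms differ by the ratio of batch volumes, 1019 / 1003 = 1.016, or under 2%. Simethicone is measured here as the volume of undyed product that the recipe lists.

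**The case against.** The case for leaving the text alone has some force. The documents do not present polysorbate 80 or simethicone as a relevant allergen; their only comment is that Tween 80 is a common food additive. They give no allergy rate, and the amounts are small. Routine history may catch a known allergy, so it would be too strong to say that such a patient could never be identified. The protocol and dosing are also stated to have been approved by the FDA IND committee. All this makes the point minor. It does not close the gap: for peppermint the protocol did not rely on routine history, but wrote a criterion, a question and a database entry. Approval adds no missing ingredient to the criterion.

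A reader might infer more than the documents support, in four ways.

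- **Excipient reactions could stop the trial.** The overall limits are more than 5 patients with the same Grade 3 event, more than 3 with the same Grade 4 or higher, or a single Grade 5 event. For illustration, assume known allergy in 1 per 1,000 patients (not a documented rate), all 300 patients dosed, and a Grade 4 reaction in every allergic patient. The expected count is 300 × 0.001 = 0.3, and the Poisson chance of 4 or more is 1 − e^(−0.3)(1 + 0.3 + 0.045 + 0.0045) ≈ 0.0003. At 1 per 10,000 it is about 3 in 100 million. One event could add to a count, but reaching these Grade 3 or Grade 4 limits this way is not realistic. In addition, the Grade 3 allergy example is specific to peppermint oil and to reactions that need hospitalization, although the list is open-ended.
- **Such reactions would be blamed on peppermint oil.** The placebo carries both excipients at nearly the same concentration, so the comparison between arms is not biased. The plan has an attribution scale for individual events.
- **All 300 patients are exposed.** The 300 includes an allowance of 300 − 274 = 26 for poor preparation or withdrawal of consent, and the first dose is given at the cecum during withdrawal. Some patients may receive none, so the accurate statement is every dosed patient.
- **The screen is pointless for the placebo arm.** It covers nothing in solution B, but screening comes before randomisation and has to serve both arms.

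**Conclusion.** The gap is real and narrow. The exclusion criterion, the allergy question and the risk section are each narrower than the ingredient lists, and under the text as written a patient with a known allergy to polysorbate 80 or simethicone is eligible and would receive it in either arm.

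It is a minor matter of patient safety and a cheap improvement. The 274 and 300 figures, the 80% power and the chi-square comparison of adenoma detection rates do not change. The conclusion rests on the stated recipes and criteria. How many patients it touches depends on an allergy rate that the documents do not give; it is assumed to be low. The consent form and telephone script were not available, but the protocol itself states the scope of the allergy question.

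**What to change.** Reconcile four places with the ingredient lists for solutions A and B: exclusion criterion 10, the pre-procedure allergy question, the REDCap field that records the answer, and the allergy item with its minimisation step in the risk section. Each should refer to known allergy to any listed ingredient of solution A or B, which adds polysorbate 80 and simethicone to peppermint. The entry in the consent form should match.

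The cost is a few words in each place and the loss of almost no eligible patients. No statistical section needs to change.

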#### **Duration of Treatment:**

Group 1 - Peppermint oil will be applied intraluminally during time taken for colonoscopy only. Group 2 – Placebo solution will be applied intraluminally during time taken for colonoscopy only.

#### **Criteria for Evaluation:**

Safety assessments will be conducted at start and finish of colonoscopy. Patients will have blood tests reviewed in the electronic medical records system and undergo standard pre-endoscopy history and physical examinations. ADRs will be calculated after colonoscopies are completed. Total time spent in colonoscopy including withdrawal time (defined as time taken to withdraw endoscope from cecum to the end of the patient's GI tract) will be recorded. The bowel-prep will be graded according to Boston bowel prep score (BPPS) and recorded for each patient.

#### Risks and discomforts and how minimized:

1) Breech of privacy - The data, while securely stored, has a small risk to be breeched and is a risk to participating in this study.

2) There is a small risk of allergy to peppermint oil, and, if encountered, we will treat accordingly to standard care protocol.

The following steps will be taken to minimize these risks are:

1) Risks of confidentiality breech will be minimized using security features as previously defined including use of a secure, online database application (REDCap) and storage of hard-copy documents in a locked cabinet in the PI's locked office.

2) Risk of allergy to peppermint oil will be minimized by asking subjects prior to the procedure for known allergies to peppermint or its byproducts.

#### **Benefits to subjects**

Currently, there are no known benefits for subjects who participate in this study.

#### Costs to the subject

There will be no cost to the subject for participation this study.

#### Alternative(s) to participation

The patient can choose not to participate in the study and proceed with standard colonoscopy as per routine protocol.

#### Payment to the subjects (include both reimbursement and incentives):

No payment or reimbursement will be provided to the patients for participation in this study.

#### Plan for obtaining informed consent

Either the primary investigator, co-investigators, or research assistants ("study personnel") will be on site to review scheduled outpatient colonoscopies on the morning of or afternoon of the scheduled procedure. Patients will be prescreened in UH Portal to determine if they meet inclusion and exclusion criteria. If identified as potential candidates, study personnel will approach patients after standard check-in procedures (changing into patient gown, review of medical history by nursing staff, intravenous line placement, etc.) have been completed. Privacy will be ensured during obtaining consent by offering to move to a private consultation room. Patients will be offered the opportunity to participate in the study with explanation of risks and benefits. They will be provided the opportunity to ask questions and will have ample time to determine whether they choose to participate. Please see the attached consent form to this of this protocol.

#### Provisions for subjects from vulnerable populations:

#### Employees of UHHS

Employees of UHHS will also be include as potential candidates for this study if they choose to participate. Extra caution will be taken to obtain consent in a private room where their decision to participate in the study or not to participate can remain discrete. In addition, we will follow the established protocol regarding deletion of identifying health information at completion of study enrollment.

#### Non-English Speaking or Illiterate Patients

There is minimal risk in participation of this study and the main purpose is to establish if there is a diagnostic benefit. If these patients are deemed candidates for inclusion into the study, the

appropriate translation and/or interpretation services will be employed to ensure complete and total understanding of the risks and benefits of participation in this study. For illiterate patients we will explain the study in clear and concise manner appropriate for the patient's level of understanding. If patients are unable to understand or provide informed consent despite these measures, they will not be included to participate in the study. It will be made clear to the patients that the care they receive will be in no way affected by participation in study and that no harm will come to them by choosing not to participate.

#### Data safety monitoring plan:

#### OVERSIGHT RESPONSIBILITIES

Oversight of the trial is provided by the Principal Investigator (PI), [name], and Drs. [name], [name], [name], and [name]. ("co-investigators" throughout).

#### MONITORING PROCEDURES

[name] assures that informed consent is obtained prior to performing any research procedures, that all subjects meet eligibility criteria, and that the study is conducted according to the IRB and FDA-approved research plan.

Study data are accessible online at all times for the PI and co-investigators to review. The PI and co-investigators review(s) study conduct including: accrual, drop-outs (if any, given that randomization will be done immediately prior to the procedure), and protocol deviations on a quarterly basis. The PI review(s) AEs individually real-time and in aggregate on a monthly basis. The PI and co-investigators review(s) serious adverse events (SAEs). The PI will visit each study site on a quarterly basis to ensure the protocol is being followed accurately at each site. The PI ensures all protocol deviations, AEs, and SAEs are reported to the IRB according to the applicable regulatory requirements. There are minimal AEs and SAEs expected however they are defined as below.

#### COLLECTION AND REPORTING OF SAEs AND AEs

For this study, the following AE definitions are used and are adapted from the National Cancer Institute (NCI) Common Terminology Criteria for Adverse Events (CTCAE):

Adverse event: Any unfavorable and unintended sign (including an abnormal laboratory finding), symptom or disease temporally associated with the use of peppermint oil during colonoscopy that may or may not be considered related to peppermint oil itself.

AEs are graded according to the following scale:

Grade 1: Mild; asymptomatic or mild symptoms such as, but not limited to: abdominal cramping, bloating, mild nausea, diarrhea, constipation, or headache that do not require any intervention.

Grade 2: Moderate; symptoms such as, but not limited to: abdominal cramping, bloating, mild nausea, diarrhea, constipation, or headache that affect and limit age-appropriate instrumental activities of daily living (ADL), which refers to preparing meals, shopping for groceries or clothes, using the telephone, managing money, etc; symptoms as above where there a minimal, local or noninvasive intervention is indicated.

Grade 3: Severe or medically significant but not immediately life-threatening symptoms such as, but not limited to: an allergic reaction without evidence of anaphylaxis to peppermint oil which would require hospitalization and therapeutic intervention; hospitalization or prolongation of hospitalization for procedure related complications, or prolongation of hospitalization indicated;

disabling; limiting self-care ADLs, which refers to bathing, dressing, and undressing, feeding self, using the toilet, taking medications, and not bedridden.

Grade 4: Life-threating consequences such as a severe allergic reaction resulting in systemic anaphylaxis; severe acute end-organ damage including, but not limited to liver or renal failure; caustic injury to mucosa resulting in perforation requiring acute endoscopic or surgical intervention; and other scenarios were urgent intervention or transfer to ICU care is initiated.

Grade 5: Death related to AE.

Our study uses the following AE attribution scale:

Not related: The AE is clearly not related to the study procedures (i.e., another cause of the event is most plausible and/or a clinically plausible temporal sequence is inconsistent with the onset of the event).

Possibly related: An event that follows a reasonable temporal sequence from the initiation of study procedures, but that could readily have been produced by a number of other factors. Related: The AE is clearly related to the study procedures.

Adverse events Grade 3 or higher will be reported to the IRB and FDA as soon as possible, but certainly within the required 15 days of the investigator being made aware of the event. In addition, all AEs are reported according to the UH IRB AE reporting guidelines.

Individual stopping criteria for study: Given the short duration of actual exposure to the interventional agent, 1.6% peppermint oil, we expect minimal

Overall stopping criteria for study:

- 1) If more than 5 patients develop the same CTCAE Grade 3;
- 2) If more than 3 patients develop the same CTCAE grade 4 or higher
- 3) If 1 or more patient develops CTCAE grade 5.

In the case that any of the above occur, the study will be stopped and the FDA and the respective IRBs will be notified of study stoppage. An investigation as to the causes for these events will ensue by the PI and co-investigators to determine if these events are related to the investigational agent, peppermint oil. The findings will be submitted to the FDA and the institutional IRBs.

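### Stopping rule 1 does not count Grade 4 cases, so a cluster of the same reaction can escape the mandatory stop by being more severe

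*Combined protocol and SAP*

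**What the plan says.** The overall stopping criteria (Collection and Reporting of SAEs and AEs) are three counts:

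- Rule 1: "If more than 5 patients develop the same CTCAE Grade 3"
- Rule 2: "If more than 3 patients develop the same CTCAE grade 4 or higher"
- Rule 3: "If 1 or more patient develops CTCAE grade 5"

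Any one is sufficient: "In the case that any of the above occur, the study will be stopped". The investigation into cause follows the stop.

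The same section places allergic reactions in two grades. Grade 3 includes "an allergic reaction without evidence of anaphylaxis to peppermint oil"; Grade 4 includes "a severe allergic reaction resulting in systemic anaphylaxis". Allergy is the only clinical risk named under Risks and discomforts: "There is a small risk of allergy to peppermint oil".

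Elsewhere the plan includes higher grades explicitly when it means them. The reporting rule reads "Adverse events Grade 3 or higher will be reported to the IRB and FDA as soon as possible", and the recall rule under Follow up after completion of procedure also covers Grade III and above.

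**The concern.** Rule 2 carries *or higher*; rule 1 does not. Read as written, the two counters are separate, and a patient whose event reaches Grade 4 does not count toward rule 1. The phrase has no effect in rule 2, because a single Grade 5 event already stops the study under rule 3. In rule 1 it would matter.

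The result is a rule that is not monotone in severity: replace one Grade 3 case in a stopping cluster by a life-threatening case of the same event, and the mandatory stop disappears. This affects the product risk the plan itself names, since a cluster of allergic reactions could well span Grades 3 and 4. A halt would then rest on the investigators' judgement, which preset thresholds are meant to avoid.

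**Working it through.** **Inputs.** From the stopping criteria: rule 1 needs at least 6 patients, rule 2 at least 4, rule 3 at least 1. From the Data Analysis Plan: 150 patients per arm, 300 in all. Event rates and the Grade 4 share are not in the documents and are assumed below. The thresholds are set counts, so there is no derived figure to reproduce.

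**Step 1: logic, with no assumptions.** Let G3 and G4 be the numbers of patients with one event at Grade 3 and Grade 4, each patient counted once at the highest grade, with no deaths.

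- As written: stop if G3 ≥ 6 or G4 ≥ 4.
- Changed: stop if G3 + G4 ≥ 6 or G4 ≥ 4.

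| G3 | G4 | Patients | As written | Changed |
|---|---|---|---|---|
| 6 | 0 | 6 | stop | stop |
| 5 | 1 | 6 | continue | stop |
| 5 | 3 | 8 | continue | stop |
| 5 | 4 | 9 | stop (rule 2) | stop |

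The most patients possible without a stop is 5 + 3 = 8 as written and 5 as changed. Exactly six combinations (G3, G4) move from continue to stop: (3,3), (4,2), (4,3), (5,1), (5,2) and (5,3).

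**Step 2: chance of escaping once six patients have the event.** With Grade 4 share f, no stop has been reached if 1 to 3 of the six are Grade 4:

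P = Σ(k = 1 to 3) C(6,k) f^k (1−f)^(6−k)

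For f = 0.25: 0.356 + 0.297 + 0.132 = 0.784 (from unrounded terms). For f = 10%, 25%, one third and 50%, P is 47%, 78%, 81% and 64%. Under the changed rule it is 0%.

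**Step 3: chance that the rules stop the study, assumed rates.** For n patients with event rate r, p3 = r(1−f) and p4 = rf:

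P(stop, as written) = 1 − Σ(a = 0 to 5) Σ(b = 0 to 3) n!/[a! b! (n−a−b)!] p3^a p4^b (1−p3−p4)^(n−a−b)

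The changed rule keeps only the terms with a + b ≤ 5. With n = 150, r = 4% and f = 0.25 (p3 = 0.03, p4 = 0.01), the results are 0.342 as written and 0.561 as changed. Events are assumed in one arm only:

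| Grade 4 share | 4%: as written | 4%: changed | 6%: as written | 6%: changed |
|---|---|---|---|---|
| 0 | 56% | 56% | 89% | 89% |
| 10% | 46% | 56% | 83% | 89% |
| 25% | 34% | 56% | 74% | 89% |
| one third | 33% | 57% | 72% | 89% |
| 50% | 41% | 60% | 77% | 90% |

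At lower rates in 150 patients, over shares of 10% to 50%, the probability is 0.2–0.7% as written against 0.4–1.0% changed at a 1% rate, and 3–7% against 8–11% at 2%.

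**Step 4: unnecessary halts.** The same formula with n = 300 and a background rate for one event, over shares of 10% to 50%:

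| Background rate | As written | Changed | Increase (percentage points) |
|---|---|---|---|
| 0.2% | below 0.03% | below 0.03% | below 0.01 |
| 0.5% | 0.2–0.7% | 0.4–1.0% | 0.2–0.3 |
| 1% | 3–7% | 8–11% | 2.7–5.5 |

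**The case against.** Five points can be made for the plan.

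- **Same event.** Non-anaphylactic reaction and anaphylaxis appear as separate examples, and nothing says they pool. If they are different events, adding *or higher* alone would not stop the five-plus-three case. That is right about the remedy, and is why a counting line is needed. It does not rescue the rule: unpooled, the cases still do not add up.
- **Missing noun.** Rule 1 does not say the same what. If it means only the same grade, six unlike Grade 3 events stop the study now, and naming the same adverse event would remove that stop. This trade-off is real if that reading was intended. But on that reading *the same* is redundant, so the same event is the natural meaning, and the Grade 4 gap exists on both readings.
- **Size.** Rates of 4% and 6% mean 6 or 9 expected cases in one arm of 150. The plan expects minimal events and excludes known peppermint allergy. At 1% the gain is at most about 0.3 percentage points. This stands: the probabilities illustrate the rule and do not forecast this trial.
- **Other safeguards.** The principal investigator reviews events in real time, and Grade 3 or higher events go to the IRB and FDA within 15 days. The events would not go unseen, but neither safeguard sets a stopping threshold.
- **Cost.** The extra halts are worked out for one event type; the total over several types is not. This also stands.

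**Conclusion.** The concern holds. Followed exactly, the rules can switch off a mandatory stop because the same reaction became more severe. That is a rule wrong as written, not a missing detail, and the 8-against-5 comparison needs no assumed rate. The probabilities rest on assumed rates and Grade 4 shares, one event type, events in a single arm and no deaths. No endpoint, sample size or analysis is affected, and the gap matters only once at least six patients share a Grade 3 or 4 event. It should still be corrected, because stopping rules exist for the outcome nobody expects.

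**What to change.** Keep all three thresholds and reword the overall stopping criteria:

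- Rule 1: *more than 5 patients with the same adverse event at CTCAE Grade 3 or higher.*
- Rule 2: *more than 3 patients with the same adverse event at CTCAE Grade 4 or higher.*
- Rule 3: unchanged.
- Added line: *each patient counts once per event, at the highest grade reached; anaphylaxis counts as an allergic reaction.*

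No relatedness filter is needed, because the plan stops first and investigates afterwards. The sponsor should confirm that the same event, rather than any event of that grade, is what was meant; *or higher* is needed either way.

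The cost is a short amendment to the IRBs and FDA, with no extra data or staff, plus the additional halts in step 4 of the working. Those can occur only after at least six patients have had the same Grade 3 or 4 event.
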